Evaluation of Cardiovascular Disease Risk in Children with Type 1 Diabetes Mellitus by Oscillometric Method and Echocardiography

Statistical analysis

All analyses were carried using SPSS 25.0 (IBM, USA). The findings of the study are expressed as frequency and percentages. Normality test was conducted using the Kolmogorov-Smirnov test. Non-normally distributed variables were presented as the median and interquartile range (IQR) with 25^{th} – 75^{th} percentiles, while variables with normal distribution are expressed as mean \pm standard deviation. Categorical variables were compared using the Chi-square test. Fischer's exact test was applied according to the percentage of expected counts. Numerical variables with and without normal distribution were compared using the independent samples t-test and Mann–Whitney U, respectively. The Kruskal–Wallis test was used to compare numerical variables without normal distribution between more than two groups. Spearman correlation analysis was performed to determine the variables associated with EFT, cIMT, AIx@75, and PWV scores and p<0.05 was considered as a statistically significant value. Multivariable logistic regression analysis was performed to detect associated factors with PWV and AIx@75.

Study Protocol

Participants of this cross-sectional, single-center study were recruited from Pediatric Endocrinology department. T1DM patients with a body mass index (BMI) between the 5th and 85th percentile according to age and gender, having this diagnosis for at least 2 years and ages 8–18 years, were consecutively included in the study. Exclusion criteria for the patient were determined to be having any chronic diseases other than T1DM and presence of a congenital and/or acquired heart disease, hypertension etc. Healthy adolescents were recruited from those who applied to the pediatric clinic for annual routine child health check-ups and were healthy. The control group consisted of 87 sex, age and BMI matched healthy children. Exclusion

criteria for the control group were determined to be having any chronic diseases and presence of a congenital and/or acquired heart disease, hypertension etc. Each subjects weight, height measurements were done and BMI was estimated.

In our study, cuff-based validated oscillometric Mobil-O-Graph device (I.E.M., GmbH, Aachen, Germany) was used to PWA. Measurements were taken from the left arm in a room after a minimum rest of 5 minutes. The cuff size was chosen based on the circumference of the middle upper arm.

Echocardiographic examinations were performed by using an ultrasound system (iE33, Philips, The Netherlands, Eindhoven), equipped with a broadband (1-5 MHz) X5-1 transducer. Echocardiographic examinations were obtained by a single experienced pediatric cardiologist blind to diabetes status of participants. Epicardial fat was identified as the echo-free space between the outer wall of the myocardium and the visceral layer of pericardium.

Measurement of cIMT was performed by the same experienced pediatric cardiologist by using Vivid E95 echocardiography machine (GE Vingmed, Horten, Norway) equipped with 9L linear probe (2,4-10 Mhz). cIMT is defined as the distance between the first echogenic line (lumen–intima interface) and the second echogenic line (media–adventitia interface) of the far wall.

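### Does letting a Kolmogorov-Smirnov test choose between the t-test and Mann-Whitney U undermine the group comparisons?

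*Combined protocol and SAP*

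**What the plan says.** All of this is in the Statistical analysis section of the combined protocol and SAP. The normality check is given in one sentence: "Normality test was conducted using the Kolmogorov-Smirnov test". The two-group rule follows from it: "Numerical variables with and without normal distribution were compared using the independent samples t-test and Mann–Whitney U, respectively". The same classification decides whether a variable is summarised by mean and SD or by median and quartiles. The section does not give the significance level of the normality test, say whether the Lilliefors correction applies, or say whether groups are tested separately or pooled. For the study as a whole, "p<0.05 was considered as a statistically significant value".

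The pre-test does not govern everything. Spearman correlation is fixed for the "variables associated with EFT, cIMT, AIx@75, and PWV scores", and logistic regression is fixed for PWV and AIx@75.

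On size, the Study Protocol section says "The control group consisted of 87 sex, age and BMI matched healthy children". Patients with type 1 diabetes "were consecutively included in the study", but their number is not given. Neither section gives an SD or a distribution for any marker.

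**The concern.** A normality p-value that selects the test also selects the hypothesis: a difference in means in one branch, a rank comparison in the other. Kolmogorov-Smirnov is a weak detector of skew. When mean and SD are estimated from the sample and no correction is made, it rejects rarely unless skew is strong. Sampling noise could then decide whether PWV, for example, is tested on means or on ranks. The four markers could end up tested on different hypotheses, and a skewed marker could be reported as mean and SD. Two analysts following the same text might run different tests. If this distorted error rates or cost power, the main comparison of patients with controls would be at risk.

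**Working it through.** The plan has no sample-size or error-rate figure to reproduce, so the check is by simulation.

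**Inputs.** Controls: 87 (Study Protocol). Patients: not stated; 87 assumed, with 50 and 120 as a range where shown. Level 0.05 (Statistical analysis), assumed two-sided and assumed for the normality test too. Marker shapes: not stated; normal, lognormal with sigma 0.15 to 0.7, gamma with shape 4, and t with 5 df are assumed.

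**Step 1: how often one sample of 87 is called non-normal.** The statistic is the largest gap between the empirical distribution and a normal curve with the sample mean and SD. The 5% critical value is 0.0955 with the Lilliefors correction and 0.1435 without.

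| Skewness | Lilliefors | Uncorrected | Shapiro-Wilk |
|---|---|---|---|
| 0 (normal) | 4.8% | 0.0% | 4.8% |
| 0.46 | 17.8% | 0.2% | 31.7% |
| 0.95 | 53.9% | 4.3% | 81.7% |
| 1.30 | 76.2% | 14.4% | 96.4% |
| 1.75 | 92.0% | 32.7% | 99.7% |

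Kolmogorov-Smirnov is indeed the weaker test.

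**Step 2: how often the rule picks Mann-Whitney.** If each group is tested and the t-test is used only when both pass, the chance is 1 − (1 − p)², with p from step 1. At skewness 0.95 with the correction this is 1 − (1 − 0.539)² = 0.787 (simulated 0.778). Without it, 1 − (1 − 0.043)² = 0.084 (simulated 0.077).

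The uncorrected version is therefore insensitive but consistent up to skewness 0.95, taking the t-test in at least 92% of studies. The corrected version varies at intermediate skew (Mann-Whitney in 32% to 78% of studies for skewness 0.45 to 0.95) and settles again by 1.3 (95%). Only at stronger skew does the uncorrected choice become variable (Mann-Whitney in 26% at skewness 1.3 and 55% at 1.75).

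**Step 3: what the rule does to error and power.** There are 87 per group and 4,000 runs per row. The Monte Carlo standard error of a 5% rate is √(0.05 × 0.95 / 4000) = 0.34 points. Each cell gives t-test / Mann-Whitney / rule with Lilliefors / rule uncorrected.

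| Shape | Type I error (%) | Power, shift 0.45 SD (%) |
|---|---|---|
| Normal | 4.7 / 4.6 / 4.8 / 4.7 | 83.6 / 82.0 / 83.7 / 83.6 |
| Lognormal, skewness 0.95 | 4.8 / 5.2 / 5.3 / 5.0 | 83.9 / 88.0 / 87.7 / 84.6 |
| Lognormal, skewness 1.3 | 4.6 / 5.0 / 5.1 / 4.8 | 84.0 / 91.7 / 91.6 / 86.7 |
| Gamma, shape 4 | 5.3 / 5.1 / 5.3 / 5.3 | 83.4 / 88.2 / 87.9 / 84.5 |
| t, 5 df | 5.1 / 5.4 / 5.4 / 5.0 | 84.7 / 91.3 / 89.3 / 85.8 |

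Over all shapes run, type I error of the rule lies between 4.6% and 5.4%. Its largest power deficit against the better fixed test is 91.25 − 89.25 = 2.0 points with the correction and 91.25 − 85.83 = 5.4 points without, both for the t shape. Against the t-test it loses nothing beyond simulation noise.

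**Step 4: against a fixed Welch test.** A separate run (lognormal sigma 0.15 to 0.4, 50 or 87 patients against 87 controls, Lilliefors in each group) gave type I error of 4.4% to 6.1% for the rule and 4.3% to 5.5% for Welch on the raw or log scale. Where the groups differ by a constant ratio, power is within about 2 to 3 points. Where they differ by a constant amount, log-scale Welch can gain more on skewed data, but that advantage depends on knowing the scale beforehand.

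**The case for a change.** The strongest case for a change has three parts.

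First, the unstated version matters. At skewness 0.95, Mann-Whitney is chosen in 78% of studies with the correction and 8% without. That is a real gap in the text. However, either route leads to a valid test, and the report will show which was used.

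Second, the choice can change a verdict. The two tests fall on opposite sides of 0.05 in 2% to 5% of null runs and 4% to 16% of runs with a 0.45 SD shift. This stands, but fixing a t-test with Mann-Whitney as sensitivity analysis leaves the same disagreements to be explained.

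Third, the hypotheses differ when spreads differ. With equal means and lognormal sigma of 0.5 against 0.3, 87 per group, the t-test rejects in 5% of runs and both Mann-Whitney and the rule in 25%. With 50 patients the figures are 9% and 21%; with 120, 4% and 28%. The distributions do differ here: with both means set to 1, the medians are exp(−0.125) = 0.882 and exp(−0.045) = 0.956. Rejection by a rank test is then not a false positive, and the plan reports medians in that branch. Nor is the choice unstable, since Mann-Whitney is picked in 96% of these runs at 87 per group. What stands is a caution on reading a rank result as a difference in means.

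The lack of an adjusted difference with a confidence interval is a separate matter and does not arise from the normality test.

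**Conclusion.** No change is needed. The plan does let a Kolmogorov-Smirnov result choose the test and the summary, and that test is weaker than Shapiro-Wilk for mild to moderate skew. It does not follow that the choice is erratic. That depends on the version used and the degree of skew, and the documents give neither. On validity there is nothing to gain: type I error stays near 5% whether the test is selected or fixed. On power, the rule matches or exceeds the t-test and gives up at most 2.0 points (corrected) or 5.4 points (uncorrected) to the better of its two tests.

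The alternative is a trade-off. Putting right-skewed markers on the log scale again requires a judgement about skew, and it would give some markers a ratio and others a difference, so it does not secure a common hypothesis. The section is also written in the past tense, so the chance to fix a scale before seeing data may have gone. Naming one comparison per marker would be tidier, and stating the version of the normality test would help readers; neither alters the soundness of the results.

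This rests on 87 patients (50 and 120 tried where shown), on the assumed shapes, and, for the error rates, on similar shapes in the two groups.

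### Does the plan need between-group differences with confidence intervals for the numerical markers?

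*Combined protocol and SAP*

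**What the plan says.** The Statistical analysis section first sets the normality check: "Normality test was conducted using the Kolmogorov-Smirnov test". The result decides the summary. Skewed variables get the median with the 25th and 75th percentiles, and "variables with normal distribution are expressed as mean" with SD. It also decides the test: "Numerical variables with and without normal distribution were compared using the independent samples t-test and Mann–Whitney U, respectively". Kruskal-Wallis is added for more than two groups. The threshold, "p<0.05 was considered as a statistically significant value", stands in the sentence on Spearman correlations and is read here as covering all tests.

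The quoted test sentence does not name the groups. That it covers patients against controls is inferred from the Study Protocol section, which states "The control group consisted of 87 sex, age and BMI matched healthy children" and, on imaging, "Echocardiographic examinations were obtained by a single experienced pediatric cardiologist blind to diabetes status of participants". The number of patients is not given, nor is any SD, target difference or list of which markers are skewed.

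No between-group difference, effect estimate or confidence interval is mentioned. The multivariable logistic regression for PWV and AIx@75 is described as a search for associated factors, not as a source of a patient-control difference.

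**The concern.** The study asks about cardiovascular risk in children with type 1 diabetes and has a healthy comparison group. A natural reading of the results is how far PWV, AIx@75, EFT and cIMT differ from controls, and a p-value does not say. When p exceeds 0.05, the data may exclude a large excess in patients or may leave it open, and only an interval separates the two.

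The worry is sharper for skewed markers. The interval that belongs with Mann-Whitney U is the Hodges-Lehmann interval, built from all pairwise differences between patients and controls. It needs individual data, so a reader with only medians and quartiles cannot compute it. If those summaries gave no usable idea of precision, the reporting gap would be a real loss.

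**Working it through.** The documents give no power calculation, effect size or SD, so there is no figure to reproduce. Two things can be checked: how much a non-significant result leaves open, and how much of the missing interval the planned summaries already supply.

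**Inputs.** Controls: 87 (Study Protocol). Patients: not stated; 40, 60, 87, 120 and 150 assumed. Two-sided 5% level assumed, since sidedness is not stated.

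**Normally distributed markers.** In SD units the unpaired 95% half-width is t(0.975, n + 85) × √(1/n + 1/87). If the observed excess is zero, the upper limit equals the half-width; if it is just short of significance, the upper limit is twice the half-width.

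| Patients n | t | √(1/n + 1/87) | Half-width (SD) | Range of upper limit (SD) |
|---|---|---|---|---|
| 40 | 1.979 | 0.1910 | 0.378 | 0.378 to 0.756 |
| 60 | 1.976 | 0.1678 | 0.332 | 0.332 to 0.663 |
| 87 | 1.974 | 0.1516 | 0.299 | 0.299 to 0.599 |
| 120 | 1.972 | 0.1408 | 0.278 | 0.278 to 0.555 |
| 150 | 1.970 | 0.1348 | 0.265 | 0.265 to 0.531 |

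If controls were matched one to one (87 pairs), the half-width is t(0.975, 86) × √(2(1 − ρ)/87): 0.301 SD at ρ = 0 and 0.252 SD at an assumed ρ = 0.3.

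The unpaired formula uses only means, SDs and group sizes. The first two are planned summaries, and the group sizes come with any report of results. For these markers nothing is lost beyond a short calculation.

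**Skewed markers.** An interval for the difference in medians can be rebuilt as

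difference in medians ± 1.96 × 1.2533 × √[Σ (IQR/1.349)²/n].

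The factor 1.2533 turns the normal-theory standard error of a mean into that of a median, and it matters. Without it, coverage would be 2Φ(1.96/1.2533) − 1 = 0.882 even for perfectly normal data, and simulated coverage falls to about 0.87 to 0.89. That shortfall comes from the wrong formula, not from skewness or from information missing in the summaries.

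With the factor in place:

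- **Gamma data** (shape 4 or 2; 40, 87 or 150 patients against 87 controls; patient SD 1.0 or 1.5 times control SD): coverage about 0.94 to 0.955, and typically 1.2 to 1.35 times as wide as the Hodges-Lehmann interval.
- **Log-normal data** (log-SD 0.5 or 1.0; 50, 87 or 150 patients; equal spread): coverage 0.947 to 0.963, and typically 1.27 to 1.59 times as wide.

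Part of the extra width arises because the two intervals estimate different things: a difference in medians, and the median of pairwise differences. The rebuilt interval is therefore close to nominal but less precise.

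**The case for a change.** The best case for a change is that it costs almost nothing. A mean difference or Hodges-Lehmann estimate with a 95% interval for four markers uses data already collected, keeps every planned test, needs no margin and can be added even after the data are seen. The omission also touches every numerical group comparison, and for skewed markers only the study team can give the exact interval that goes with Mann-Whitney U.

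All of that stands as advice on good reporting. It does not show a fault in the plan. The harm would be a non-significant marker read as evidence of no difference, and the documents make no such claim. The plan's silence does not mean the report will omit intervals; this is a short methods summary, and analysts commonly add them. The half-widths above do not show harm either: with no SD or important difference stated for any marker, they cannot be called large or small.

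One reservation stays open. The controls are called matched while the tests are for independent samples, and the documents do not say whether matching was individual. Nothing here vouches for the p-values on that score; it is a separate matter from whether an interval is printed.

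**Conclusion.** The observation is correct: no between-group difference or confidence interval is mentioned for the numerical markers. No change follows, because the gap is one of presentation and leaves the planned comparisons as they are. For normal markers the unpaired interval follows from the planned summaries and group sizes. For skewed markers a near-nominal interval can be rebuilt, at a price of typically 20% to 35% extra width under the assumed gamma distributions, and up to about 59% under the more skewed log-normal ones. Printing the differences with intervals would be a courtesy to readers, and sensible analysts may do so without an instruction.

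This rests on assumed patient numbers of 40 to 150, assumed distribution shapes and SD ratios, a two-sided 5% level, and the inference that the two-sample tests cover patients against controls. It would need another look if a report presented a non-significant marker as proof of no difference.

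### EFT and cIMT at ages 8–18: crude Spearman correlation is the only stated analysis of correlates, so a variable that merely tracks age is not separated from one that holds at a given age

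*Combined protocol and SAP*

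**What the plan says.** The Statistical analysis section names one method for finding correlates of the four vascular and cardiac measures: "Spearman correlation analysis was performed to determine the variables associated with EFT, cIMT, AIx@75, and PWV scores". The sentence that follows takes two of the four further: "Multivariable logistic regression analysis was performed to detect associated factors with PWV and AIx@75". The covariates of that model are not listed. The other tests named (chi-square, Fisher's exact, t-test, Mann–Whitney U, Kruskal–Wallis) are unadjusted comparisons.

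In the Study Protocol section, patients are 8 to 18 years old and diagnosed at least two years earlier. BMI eligibility is defined relative to age, "between the 5th and 85th percentile according to age and gender", and controls are matched on age: "The control group consisted of 87 sex, age and BMI matched healthy children". The number of patients is not given.

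The measurement paragraphs describe physical quantities: "cIMT is defined as the distance between the first echogenic line", and "Epicardial fat was identified as the echo-free space between the outer wall of the myocardium and the visceral layer of pericardium". They mention no age-standardised value. The text does not list the variables entered into the Spearman analysis, and does not say whether it was run in patients only or in patients and controls together.

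**The concern.** Participants range from mid-childhood to the end of adolescence. If EFT or cIMT changes over that range, any variable that also changes with age will correlate with it, whether or not the two are linked among children of the same age. Diabetes duration is the natural example, but it is an assumed one. The documents mention duration only in the eligibility rule ("having this diagnosis for at least 2 years and ages"), which permits a link with age without forcing one.

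At stake is how the list of correlates is read. For EFT and cIMT the crude correlation is the end of the stated analysis. A reader could not tell a correlate that only reflects growing older from one that would matter when comparing two children of equal age. The plan itself takes account of age elsewhere, in the BMI criterion and in the matching.

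**Working it through.** **Stated analyses, by outcome**

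| Outcome | Crude Spearman | Multivariable model | Age-standardised value stated |
|---|---|---|---|
| EFT | yes | no | no |
| cIMT | yes | no | no |
| PWV | yes | yes, covariates not listed | no |
| AIx@75 | yes | yes, covariates not listed | no |

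The documents give no sample-size or power figure, so there is nothing of the plan's own to reproduce. What follows is an illustration.

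**Inputs**
- From the documents: age 8–18, duration at least 2 years, significance at p<0.05.
- Assumed: two-sided test; correlations in patients only; n = 87 patients (borrowed from the control count); age uniform over 8–18; outcome linear in age; no effect of duration given age; age–outcome r of 0.1 to 0.6.
- Assumed duration patterns: unrelated to age (uniform 2–7 years, rho 0.00); weakly related (2 years plus an exponential with scale 5, truncated at age minus 1, rho 0.16); moderately related (uniform from 2 to age minus 1, rho 0.39).

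**Step 1: correlation induced by age alone.** With no link given age, crude rho ≈ rho(duration, age) × r(age, outcome).
- Weak: 0.16 × 0.3 / 0.5 / 0.6 = 0.048 / 0.080 / 0.096 (simulated means 0.048 / 0.081 / 0.098).
- Moderate: 0.39 × 0.3 / 0.5 / 0.6 = 0.117 / 0.195 / 0.234 (simulated means 0.114 / 0.192 / 0.235).

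**Step 2: what reaches p<0.05.** The critical |rho| is t/√(df + t²). With df = 85 and t = 1.988, this is 1.988/√(85 + 3.95) = 0.211. A weak correlation is therefore enough.

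**Step 3: how often that happens.** Simulation with 10,000 data sets per cell:

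| Duration–age rho | Crude p<0.05 at r = 0.3 / 0.5 / 0.6 | Age-partial p<0.05 |
|---|---|---|
| 0.00 | 4.7% / 5.2% / 5.0% | 4.7% / 4.9% / 5.0% |
| 0.16 | 7.8% / 11.9% / 14.9% | 5.3% / 5.3% / 5.2% |
| 0.39 | 18.3% / 43.4% / 59.8% | 5.1% / 5.2% / 4.8% |

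A hand check of the largest cell by Fisher's z: atanh(0.234) × √84 = 0.2384 × 9.165 = 2.185, and Φ(2.185 − 1.96) = Φ(0.225) ≈ 0.59, in line with 59.8%.

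At r = 0.1 the crude rate is close to nominal, about 5% (weak) and 6% (moderate).

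**Step 4: sensitivity.** For duration–age rho 0.39, the crude rates at r = 0.3 / 0.5 / 0.6 are 12.3% / 27.5% / 37.5% with n = 50 and 23.7% / 57.5% / 74.2% with n = 120. Curved age relations (sigmoid or accelerating) at n = 87 give 6.7–14.2% (weak) and 16.8–56.9% (moderate). The age-partial rate stays between 4.6% and 5.5% in all of these.

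**Step 5: cost in power if duration has a real effect** (assumed 0.3 SD per SD, n = 87, range over r = 0.3 to 0.6):

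| Duration–age relation | Age-partial detects | Crude detects |
|---|---|---|
| Unrelated | 79–90% | 75–76% |
| Weak | 71–83% | 82–90% |
| Moderate | 68–81% | 95–100%, part of it the age effect |

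**The case against.** **The plan claims only association.** A crude correlation answers that question correctly, and age adjustment answers a different one. This stands, and it is why the point is minor. A reader might infer from the 60% figure that the Spearman test produces false positives. It does not: where duration and outcome both follow age, they really are correlated marginally, and the test detects that.

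**Age may be among the variables correlated.** The list is not given, so this is possible. Under the model above, age's own correlation with the outcome would be significant in about 80% of data sets at r = 0.3 and nearly all at r = 0.5 or more. A reader would then usually see a warning. It would therefore be too strong to say that the role of age stays hidden. What remains is that two separate crude correlations do not show how much of one is explained by the other.

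**The premise is not in the documents.** They do not say that EFT or cIMT varies with age in this sample, that duration was examined, or that the analysis was confined to patients (duration is undefined for controls). This stands; the supportable range starts at no problem.

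**'Scores' may mean age-standardised values.** The measurement paragraphs do not exclude this, since a standardised score also starts from a measured distance. But the text states no standardisation, and the same word covers PWV and AIx@75.

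**PWV and AIx@75 may be no better off.** A reader might infer from the multivariable model that those two are adjusted for age. With its covariates unlisted, that is not established. The point on EFT and cIMT does not depend on it.

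**Conclusion.** The point holds in a limited form. For EFT and cIMT the stated analysis of associated variables stops at crude Spearman correlation, so a correlate that only tracks age is not separated from one that holds at a given age.

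The size cannot be determined from the documents. Under the assumptions listed, including patients only and n = 87, age alone would make duration a significant correlate in anything from the nominal 5% to about 60% of data sets, with induced correlations no larger than about 0.24 on average.

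Two further readings are tempting and unsupported. One is that age distorts the comparison of patients with controls: the groups are matched on age, and nothing here touches that comparison. The other is that the eligibility rule ties duration to age: a pattern with no relation at all fits the rule equally well.

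This is a low-severity improvement to an exploratory analysis. If the values analysed are age-standardised, the point disappears.

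**What to change.** For each of EFT and cIMT, add one age-adjusted analysis to the Statistical analysis section: either a Spearman correlation partial on age, or a multivariable linear regression that includes age. Report it beside the crude correlations, which stay as description. State whether the analysis is in patients only or in the pooled sample. Adding sex is optional; matching controls on sex is not in itself a reason to adjust correlations among patients. The past-tense text suggests that the analysis may be done, in which case label the addition post hoc. If 'scores' does mean age-standardised values, one sentence saying so is enough.

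The cost is one or two sentences and one extra analysis per outcome, using age data that the matching already required. Some crude associations may weaken, power falls where a variable is related to age, and a post hoc result carries less weight.

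### The only multivariable model is logistic regression for PWV and AIx@75, but no classes or cut-point are defined for these numerical measures

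*Combined protocol and SAP*

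**What the plan says.** The combined protocol and SAP describes one adjusted analysis, in its Statistical analysis section: "Multivariable logistic regression analysis was performed to detect associated factors with PWV and AIx@75". The sentence before it covers the same two measures: "Spearman correlation analysis was performed to determine the variables associated with EFT, cIMT, AIx@75, and PWV scores", with the criterion that "p<0.05 was considered as a statistically significant value". Group comparisons are described only for numerical variables in general.

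The Study Protocol section says that a "cuff-based validated oscillometric Mobil-O-Graph device (I.E.M., GmbH, Aachen, Germany) was used to PWA" and gives the measurement conditions. It also defines epicardial fat and cIMT. It does not say what would count as a raised or abnormal PWV or AIx@75. The percentiles in the document are the BMI entry range and the interquartile range used for description. The one sample size is for controls: "The control group consisted of 87 sex, age and BMI matched healthy children". The number of patients is not given.

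**The concern.** A logistic model cannot be fitted to a measured quantity until that quantity has been put into classes. The plan does not say whether two classes, ordered classes or no classes were meant, nor where any boundary lies. Several different analyses are consistent with the sentence, and they need not find the same factors.

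No other multivariable analysis is named, so the adjusted findings for PWV and AIx@75 rest on this one. Categorising a continuous outcome usually discards information, and a cut left open can be chosen after seeing the results. The Spearman analyses are not affected. The group comparisons should not be either, although the sentence describing them does not name PWV or AIx@75.

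**Working it through.** **1. Text.** The document states no power, effect size or event count for this model, so there is no figure to reproduce. Side by side, the Spearman sentence treats PWV and AIx@75 as ordered numerical scores, the next sentence treats them as categorical, and nothing in between or in Study Protocol links the two.

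**2. Information kept after a split.** Assume the outcome is normal given the covariates, and that effects are weak (these are limiting values).

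- Two classes cut at quantile p: φ(z_p)² / [p(1−p)]. This gives 0.637, 0.539 and 0.342 at p = 0.50, 0.75 and 0.90, so losses of about 36%, 46% and 66%.
- Ordered classes: the sum over classes of (φ(a) − φ(b))² / P(class), where a and b are the class limits. This gives 0.793 for tertiles (21% lost) and 0.861 for quartiles (14% lost).
- Heavier tails, against linear regression on the raw scale: f(q)² × variance / [p(1−p)]. At the median this is 0.757 for a t distribution with 10 df (24% lost) and 0.961 with 5 df (4% lost). It then passes 1: 1.125 with 4 df and 1.62 with 3 df, where a median split does better than raw-scale linear regression.

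**3. Power for one factor (illustration, all inputs assumed).** Take n = 87 patients, set equal to the control count, and y = 0.4c + bx + e with normal e, one covariate c and b = r/√(1−r²). At r = 0.30, b = 0.30/√0.91 = 0.314. The outcome is cut at the sample quantile. The linear t-test is compared with the logistic Wald test, two-sided at 0.05 (the document does not state sidedness), in 6000 data sets per cell (standard error at most 0.65 points).

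| Partial r | Linear | Logistic, median | 75th | 90th |
|---|---|---|---|---|
| 0.20 | 46% | 29% | 24% | 16% |
| 0.30 | 81.3% | 57.6% | 49.5% | 32.5% |
| 0.40 | 97% | 84% | 76% | 53% |

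At r = 0 the rejection rate was 4.2% to 5.6%, so the comparison is fair. The upper class would hold about 87 × 0.50 = 43, 87 × 0.25 = 22 and 87 × 0.10 = 9 children.

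Sensitivity at r = 0.30, linear against median split:

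| n | Linear | Median split | Gap (points) |
|---|---|---|---|
| 50 | 55.6% | 34.0% | 21.6 |
| 60 | 64.6% | 41.3% | 23.3 |
| 87 | 81.3% | 57.6% | 23.7 |
| 120 | 91.8% | 73.4% | 18.4 |
| 174 | 98.4% | 87.6% | 10.8 |

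**4. Does the cut change the finding?** In the n = 87 setting, the p<0.05 verdict on the same factor differed between the median and 75th-percentile cuts in 7.7%, 12.7%, 25.8%, 32.3%, 22.4% and 7.2% of data sets at r = 0, 0.1, 0.2, 0.3, 0.4 and 0.5. The three cuts did not all agree in 11.5% to 54.7%. The peak near r = 0.30 belongs to n = 87. At n = 174, disagreement between the first two cuts was greater at r = 0.20 (33%) than at r = 0.30 (19%).

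For a whole list, a second simulation used five covariates with standardised effects 0.30, 0.25, 0.20, 0.20 and 0 (1000 data sets per n). The set of significant factors differed between the median and 75th-percentile cuts in 80% of data sets at n = 87 and 75% at n = 174. It was not identical across all three cuts in 95% at either n.

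**The case against.** The strongest reply is that what is proven is a gap in definition, not a wrong analysis. The word may be a slip for linear, in which case nothing is lost. If raised versus not raised stiffness was meant, which a title about cardiovascular risk allows, logistic regression answers a different question, and power for a mean difference is not a like-for-like comparison. Stating the classes and their source would then be enough. The slip reading stands as a possibility, and the document does not settle it. The second reading has no support in the text, which defines no raised class for either measure.

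The sizes rest on assumptions: only the 87 controls come from the document. That stands, and the figures are illustrations. Some of the disagreement between cuts is simply low power. With very heavy tails a median split can beat raw-scale linear regression, so categorising *usually* loses information; it does not always.

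The candidate covariates, the selection rule and whether controls enter the model are also unstated, so changing the model does not by itself fix the list of factors. That is true, but it is a separate gap.

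**Conclusion.** The concern holds. The plan's only adjusted analysis cannot be carried out as written, because its outcome is undefined for two measures that the plan elsewhere handles as numbers. This conclusion rests on the text alone and is firm.

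The size is conditional on categorising. With an outcome that is normal given the covariates, two classes cost about a third to two thirds of the information, depending on the cut, and ordered tertiles or quartiles cost about a fifth to a seventh. With 87 patients and a partial correlation of 0.30, power would fall from about 81% to between 32% and 58%, and about one verdict in three would change between two ordinary cuts. The true figures depend on the number of patients, the effects and the outcome distributions, none of which the document gives. This should be fixed; it does not undermine the unadjusted analyses.

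**What to change.** In the Statistical analysis section, replace the logistic sentence with multivariable linear regression of PWV and of AIx@75 as continuous outcomes, reporting coefficients with 95% confidence intervals. If residuals are skewed, use robust standard errors, or a log transformation where all values are positive. Keep any logistic model as secondary, with its classes and cut-point stated and justified independently of these data. If the word was a slip for linear, correct it and say so.

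The cost is one sentence and two models on the same data and software. Results become mean differences instead of odds ratios. Because the text is in the past tense, a logistic analysis may already exist; if so, the linear models should be reported as a change made after it.
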